### 9.2.7 Device Related Adverse Events and Device Malfunctions

All device related adverse events and device malfunctions must be reported as complaints to HeartWare's Quality group.

All device malfunctions as defined by INTERMACS™ will be recorded in the INTERMACS™ database according to their Manual of Operations.

### 9.2.8 Additional data collection

#### Post-Transplant

Additional information will be collected to evaluate the effect of the lateral surgical procedure on the pre and post-operative requirements, length and severity of the hospitalization during the procedure and length of hospitalization post-transplant.

The following parameters will be included:

1. Total operative time
2. Cardiopulmonary Bypass time
3. Intraoperative blood/ coagulation products
4. If the surgical procedure was done on a Virgin Chest
5. If the patient had Pneumothorax
6. Severity of pericardial/pleural adhesions
7. Time on ventilator/inotropes
8. Total Days on Intensive Care Unit
9. Total Days in Hospital after transplant

The additional data will be collected on transplanted patients only.

The additional data will not be captured in INTERMACS database.

#### Follow-Up after stroke if transplanted or explanted

Additional information will be collected for all stroke patients who are transplanted or explanted in order to assess mRS ( $\geq 3$  months post-stroke) to classify them for the primary endpoint.

The following parameters will be included:

1. Date of assessment
2. mRS

The additional data will be collected only on transplanted or explanted patients who had a stroke with mRS  $\geq 4$  less than 3 months prior to the transplant or explant.

The additional data will not be captured in INTERMACS database.

## 10. SURGICAL IMPLANT PROCEDURE

### 10.1 Pre-Implant Device Management

Refer to the HeartWare® HVAD Instructions for Use for detailed equipment set-up procedures.

### 10.2 Implant Procedure

Refer to the Instructions for Use for the thoracotomy implant procedure, which describes HeartWare® HVAD placement in the pericardial space, cannulation techniques and tunneling of the percutaneous lead.

### 10.3 Postoperative Patient Management including Blood Pressure (BP) Management

Refer to the HeartWare® HVAD Instructions for Use for postoperative patient management guidelines.

HeartWare strongly recommends BP Management for all implanted subjects. Since the HVAD® Pump provides continuous flow, resulting in narrow arterial systolic/diastolic pulse pressures, monitoring of the mean arterial pressure (MAP) is important. The recommended MAP target for subjects supported by the HeartWare® HVAD is < 85 mmHg (as tolerated).

## 11. STATISTICAL CONSIDERATIONS

### 11.1 Study Endpoints and Hypotheses

#### 11.1.1 Analysis Populations

The Intent-to-Treat (ITT) subject population will include all enrolled subjects intended to receive the HVAD® pump via thoracotomy at the time of skin incision.

The Per-Protocol (PP) subject population will include all ITT subjects who were implanted with the HVAD pump® via thoracotomy, on-pump, and with outflow to the ascending aorta. Sample size requirements reflect the minimum number of subjects needed for the PP population.

The primary analysis population is the PP population. All endpoints will be assessed on the ITT and PP populations.

#### 11.1.2 Primary Endpoint

The primary endpoint is success at 6 months defined as all enrolled and implanted subjects:

- Alive on the originally implanted device at 6 months, and the subject has not had a stroke with a modified Rankin Scale  $\geq 4$  (assessed  $\geq 3$  months post stroke event); or
- Transplanted by Month 6, and the subject has not had a stroke with a modified Rankin Scale  $\geq 4$  (assessed  $\geq 3$  months post stroke event), or
- Explanted for recovery by Month 6, and the subject has not had a stroke with a modified Rankin Scale  $\geq 4$  (assessed  $\geq 3$  months post stroke event).

All subjects with stroke events from implant to Month 6 will be required to remain in follow-up until the post-stroke mRS measure ( $\geq 3$  months post stroke event) is obtained, even if this occurs after the 6-month visit. If a stroke subject is alive at 6 months, but dies before the post-stroke mRS is obtained, the subject will be considered a failure with regard to the primary endpoint.

Hypothesis:

$$H_0: \pi_T \leq 77.5\%$$

$$H_a: \pi_T > 77.5\%$$

$\pi_T$  = the expected proportion of subjects experiencing success for the Thoracotomy group

The success prevalence in the thoracotomy group will be statistically compared to the performance goal (77.5%) using an exact binomial test (i.e., the lower 95% one-sided confidence limit will be greater than 77.5%). Success will be met if the lower bound of the one-sided exact 95% confidence limit is greater than 77.5%.

#### 11.1.3 Secondary Endpoint

CONFIDENTIAL

## 11.2 Sample Size Justification

### **Primary Endpoint:**

Success at 6 months is estimated to be 86% compared to a performance goal of 77.5%. Using an exact binomial test, with a one-sided alpha of 0.05, and 80% Power, a sample size of 145 implanted subjects is required.

The target success estimate of 86% is based on the following:

- The primary endpoint observed in the final BTT IDE Report for the more recent BTT CAP population (N=242), resulted in a success prevalence of 85.8% (205 out of 239 eligible subjects) for sternotomy subjects.
- Post-approval data from the INTERMACS Registry (through Q2 2014), indicates similar results for the sternotomy population of 88.0% (396/450) with a lower prevalence of success for the small subset of thoracotomy (83.3%, 55/66) and thoracotomy on-pump (82.6%, 38/46) subjects.
- The INTERMACS Federal Partners Report (from Q1 2014) indicates an 85% Kaplan-Meier survival estimate at 6 months. This is not the same as “success” in that post-exchange survival is considered.
- The INTERMACS Industry Report for HeartWare (from Q2 2014) indicates an 88% Kaplan-Meier survival estimate at 6 months. This is not the same as “success” in that post-exchange survival is considered.

Success will be met if the lower bound of the one-sided exact 95% confidence limit is greater than 77.5%.

For exploratory purposes, the primary endpoint will also be assessed and observed by:

- Site
- CPB (on pump, off pump)
- Outflow location

### **Secondary Endpoint:**

The mean length of initial hospital stay is estimated to be 26.1 days with a standard deviation of 22.8 days and a median of 20 days based on data from the BTT CAP population (N=242). Using a one sample t-test, with a one-sided alpha of 0.05, a sample of 145 implanted subjects with an average value of 21.3 days or less will result in Power greater than 80%.

Due to the skewed nature of this data, a non-parametric test (one-sample Sign test with a one-sided alpha of 0.05) to assess a reduction in median days (from the estimated 20 days) will also be conducted for support.

For exploratory purposes, the secondary endpoint will also be assessed and observed by:

- Site
- CPB (on pump, off pump)

- Outflow location

The sample size calculations were performed using nQuery Advisor®.

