2.1. Sample Size Estimate and Justification

2.1.1. Sample Size

Success at 6 months is estimated to be 86% compared to a performance goal of 77.5%. Using an exact binomial test, with a one-sided alpha of 0.05, and 80% Power, a sample size of 145 implanted subjects is required.

The target success estimate of 86% is based on the following:

- The primary endpoint observed in the final BTT IDE Report for the more recent BTT CAP population (N=242), resulted in a success rate of 85.8% (205 out of 239 eligible subjects) for sternotomy subjects.

- Post-approval data from the INTERMACS Registry (through Q2 2014), indicates similar results for the sternotomy population of 88.0% (396/450) with a lower rate of success for the small subset of thoracotomy (83.3%, 55/66) and thoracotomy on-pump (82.6%, 38/46) subjects.
- The INTERMACS Federal Partners Report (from Q1 2014) indicates an 85% Kaplan-Meier survival estimate at 6 months. This is not the same as “success” in that post-exchange survival is considered.

Success will be met if the lower bound of the upper one-sided exact 95% confidence interval is greater than 77.5%.

The mean length of initial hospital stay is estimated to be 26.1 days with a standard deviation of 22.8 days and a median of 20 days based on data from the BTT CAP population (N=242). Using a one sample t-test, with a one-sided alpha of 0.05, a sample of 145 implanted subjects with an average value of 21.3 days or less will result in power greater than 80%.

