2.4.2. Secondary Endpoint

The secondary endpoint is improvement in the length of initial hospital stay (initial recovery and step down unit) for all enrolled and implanted subjects, which is calculated by considering the number of days in acute care (ICU/CCU) plus the number of days in intermediate/step-down care (both variables taken as reported directly by INTERMACS), comprising the total number of days post-implant to discharge.

It is estimated that the mean length of initial hospital stay is 26.1 days for median sternotomy patients and thus the relevant hypotheses for this endpoint for each cohort are given by

$$H_0: \mu_T \geq 26.1$$

$$H_a: \mu_T < 26.1$$

where μ_T = the mean length of initial hospital stay for the Thoracotomy Implant Technique of the HVAD.

This secondary endpoint will be calculated and tested for each cohort using an upper tail one-sided t-test at 0.05 level of significance. Due to the skewed nature of this data, a one-sample sign test with an upper tail one-sided level of confidence of 0.05 will be conducted as supportive analysis.

The number and percentage of subjects with re-hospitalization after the initial hospitalization will be tabulated. Cumulative length of re-hospitalization after initial hospital stay (LOS) overall will be summarized using descriptive statistics, including 95% confidence intervals for the means.

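### The length-of-stay t-test is worded for the wrong tail and, under skewed shapes matching the plan's own figures, runs at about 6.7–8.2% one-sided error, not 5%

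*Protocol*

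**What the plan says.** Protocol 11.2 (repeated in the Study Summary) and SAP 2.1.1 give the planning figures for initial stay from the BTT CAP sternotomy population (N=242): "estimated to be 26.1 days with a standard deviation of 22.8 days and a median of 20 days". The test is set out as "Using a one sample t-test, with a one-sided alpha of 0.05, a sample of 145 implanted subjects", and the power statement reads "with an average value of 21.3 days or less will result in Power greater than 80" per cent. Protocol 11.1.1 adds that "Sample size requirements reflect the minimum number of subjects needed for the PP population", so 145 is a floor for the analysed set.

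The hypotheses are in SAP 2.4.2: the null is a mean of at least 26.1 days, the alternative a mean below 26.1. The same section says the endpoint will be tested "using an upper tail one-sided t-test at 0.05 level of significance".

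Both documents acknowledge skewness. The SAP wording is "Due to the skewed nature of this data, a one-sample sign test", again described as upper tail and given a supportive role only. Protocol 11.2 applies the sign test to a reduction in the median from 20 days. Neither document corrects the t-test for skewness or adjusts its critical value.

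**The concern.** Only a low t statistic can support a mean below 26.1, so the claim depends on the lower tail. In right-skewed data the sample mean and sample SD are positively correlated. Samples that happen to miss the long stays have both a low mean and a small standard error, and this makes the lower tail of t too heavy. The distortion shrinks only as 1/√n, so 145 subjects do not remove it.

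The bias runs toward declaring a shorter stay when there is none. Shorter hospitalization is one of the benefits listed in Protocol 12.1, and this is the only formal test against a sternotomy figure visible in the documents. SAP 2.4 makes no multiplicity adjustment, so the nominal 0.05 is the only error control stated for this claim.

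**Working it through.** **Inputs.** Mean 26.1, SD 22.8, median 20, alternative mean 21.3, n=145, one-sided alpha 0.05 (Protocol 11.2, SAP 2.1.1); direction from the alternative in SAP 2.4.2. The shape of the distribution is not given and is an assumption. So is the use of the sternotomy shape for thoracotomy stays under the null.

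**1. The plan's own figure.** Noncentrality = (26.1 − 21.3)/22.8 × √145 = 4.8/22.8 × 12.04 = 2.535. With 144 degrees of freedom the one-sided normal-theory power is 81.0%. The stated power above 80% reproduces.

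**2. How skewed the reference data are.**
- Lognormal with the stated mean and SD: σ² = ln(1 + (22.8/26.1)²) = 0.567; median = 26.1 × exp(−0.567/2) = 19.7; skewness 3.3.
- Gamma with the same mean and SD: k = (26.1/22.8)² = 1.31; skewness = 2/√1.31 = 1.75; median 19.8.

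Both come close to the stated median of 20.

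**3. First-order formula for the lower-tail error.** Error ≈ α + φ(z) × skewness × (2z² + 1)/(6√n), with z = 1.645 and φ(z) = 0.1031. The multiplier of skewness is 0.1031 × 6.41/72.25 = 0.00915.
- Skewness 1.75: 0.05 + 0.016 = 6.6%.
- Skewness 3.29: 0.05 + 0.030 = 8.0%.

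**4. Simulation** (at least 200,000 trials per shape, n=145, true mean exactly 26.1, nominal 5%):

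| Shape | Matched to | Lower-tail rejection |
|---|---|---|
| Normal (check) | mean, SD | 5.0% |
| Weibull | mean, SD (median 19.9) | 6.7% |
| Gamma | mean, SD (median 19.8) | 6.8% |
| Shifted gamma | mean, SD, median | 6.7% |
| Shifted lognormal | mean, SD, median | 7.6% |
| Lognormal capped at 183 days, rescaled | mean | 7.7% |
| Lognormal | mean, median (SD 21.9) | 8.0% |
| Lognormal | mean, SD (median 19.7) | 8.2% |

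The range is 6.7–8.2%. As ratios, 6.7/5 = 1.34 and 8.2/5 = 1.64; as differences, 1.7 and 3.2 points. The opposite tail rejects only about 3–4%. At n=500 the rate is still 6.7% (lognormal) and 5.8% (gamma). A heavier-tailed log-logistic gives 10.3%, but its median of 21.2 fits the stated 20 less well, so it is left out of the range.

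**5. Skewness-robust alternatives, lognormal and gamma, same n.**

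| | Ordinary t | Bootstrap-t | Johnson's modified t |
|---|---|---|---|
| Error at mean 26.1 | 6.7–8.2% | about 4.5–6.1% | 5.1–5.9% |
| Power at 21.3, every stay 4.8 days shorter, SD 22.8 | 78–79% | 70–74% | 69–74% |

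The bootstrap-t error comes from separate runs of 2,000–3,000 trials with a Monte Carlo standard error of 0.4–0.5 points, so it is only roughly located. If instead all stays shorten in the ratio 21.3/26.1, the SD falls to 22.8 × 21.3/26.1 = 18.6, and robust power is about 81–87% (ordinary t 88–90%).

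**6. The benchmark's own error.** The standard error of 26.1 is 22.8/√242 = 1.47 days. If both populations share one mean, the variance of the statistic grows by 1 + 145/242 = 1.60. The rejection rate under normal data is then Φ(−1.645/√1.60) = Φ(−1.30), about 9.7%, and about 11–13% with skewed data. No one-sample correction for skewness removes this part.

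**The case against.** The strongest reply is that a t-test on a mean at n=145, with the skew acknowledged and a distribution-free test prespecified beside it, is a conventional choice, and that an excess of two or three points on a secondary endpoint is modest. The point about size stands and limits the severity. The point about the sign test does not: it is supportive, it addresses the median, and nothing makes the claim depend on it.

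It can also be said that the documents give no distributional shape. That stands. A reader might infer that the real false-claim rate is known to be 7–8%. The documents support only a range under assumed shapes, and gamma and Weibull fits, at the low end, agree with the stated median slightly better than the lognormal matched to mean and SD. A reader might also take the ratio of 1.3–1.65 as the size of the excess. It is the ratio of the total rate to 5%.

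A third reply is that a robust test would not secure a 5% error rate for superiority over sternotomy, because 26.1 is itself an estimate. That is correct (step 6). The corrected level refers only to a mean below the constant 26.1.

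Finally, the robust test costs power in the scenario the plan used for its calculation. That is true, and the cost should be stated. Part of the ordinary t-test's power there comes from its excess error.

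**Conclusion.** The concern holds in a limited form. Read in the direction of its own alternative, the deciding test has an estimated one-sided error of about 6.7–8.2% against the stated 5%. This rests on two assumptions: a right-skewed shape consistent with mean 26.1, SD 22.8 and median of about 20, and the same shape for thoracotomy stays under the null. Every skewed shape tried exceeded 5%, and the error favours the claim.

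Separately, and without any assumption, the upper-tail wording in SAP 2.4.2 contradicts the alternative in the same section. Read literally it could not show a reduction. The stated alternative and the aim of improvement make a drafting slip the natural reading, so it would be wrong to infer that the sponsor means to test for longer stays.

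Two further inferences are not supported. The sample-size arithmetic is not wrong, since 81.0% reproduces. The primary endpoint is not touched, since it uses an exact binomial test. For a secondary endpoint with an excess of this size, the change should be made but is not a condition for the trial's main conclusion.

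**What to change.** In SAP 2.4.2 and Protocol 11.2:

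1. Correct the tail wording for both the t-test and the sign test so that it agrees with the alternative of a mean below 26.1 and with a reduction in the median.
2. Declare improvement only if the one-sided 95% upper limit for the mean from a bootstrap-t (seed and number of resamples fixed in advance) is below 26.1. Alternatively, name Johnson's modified t, rejecting in the lower tail at 0.05. Choose one before the data are analysed.
3. Keep the ordinary t-test as descriptive and the sign test as support.
4. Replace the single power statement at 21.3 days with about 70–74% (every stay 4.8 days shorter, SD unchanged) and about 81–87% (proportional shortening), naming the assumed shapes.
5. State that 26.1 is a fixed performance goal and that its sampling error from N=242 is not covered by the stated error rate.

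Before any of this, reconcile the variable itself: SAP 2.4.2 counts days from implant to discharge, while SAP 3.2 counts from the hospitalization date before implant.

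The cost is SAP and protocol wording and a few lines of code. The real price is power: about 5–9 points in the fixed-SD scenario, which takes it below the planned 80% unless the sample is enlarged or the lower figure is accepted.

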### 11.3 Site Poolability

The primary and secondary endpoints will be performed on pooled data, however, an Analysis Site poolability assessment will be incorporated into the design of the study. This will involve pooling sites into “Analysis Sites” with a target size of 5 subjects. Sites with at least 5 subjects will serve at their own Analysis Site. Those with less than 5 will be rank ordered by size and sorted secondarily by site identification number to break ties. Starting with the smallest investigative site, subjects are combined site by site until at least 5 subjects are identified, thus establishing an Analysis Site. The next Analysis Site is formed similarly to contain at least 5 subjects. The process continues until all sites and subjects are accounted for. If the last Analysis Site has fewer than 5 subjects, it is combined with the most recently created previous Analysis Site.

A Fisher’s exact test will be performed to test the homogeneity of success at 6 months across Analysis Sites. Analysis Site homogeneity is defined if the p-value is 0.15 or greater. If there is an Analysis Site effect (p-value < 0.15), an investigation of prognostic factors (i.e., baseline characteristics, medical history or other covariates of interest) will be reviewed to understand variability between Analysis Sites. As a supplemental analysis, a logistic regression model will be performed to estimate the probability of success controlling for Analysis Site and the selected prognostic factors.

### 11.4 Handling of Missing Outcomes

Every effort will be made to gather all data associated with the primary, secondary and additional endpoints. A complete case analysis, which includes all subjects with complete follow up will be conducted as the primary analysis of the primary endpoint.

[REDACTED]

[REDACTED]

[REDACTED]

- [REDACTED]
- [REDACTED]
- [REDACTED]

[REDACTED]

[REDACTED]

If a subject experiences a stroke and subsequently completes the 6 month follow-up, a post-stroke (greater than 6 months post-event) mRS is still required. If the subject dies prior to the post-stroke mRS but after the 6 month follow-up, the outcome will be considered a failure.

For the secondary endpoint, imputation for missing data regarding duration of hospital stay (in days) will not be performed.

## 11.5 Early Submission

Early review of the data will be performed when the first 100 subjects complete 6 months of follow-up. Analysis of the results will follow the Haybittle-Peto methodology, where the interim look will involve an alpha level of 0.001, retaining an alpha level of 0.05 for the final analysis of 145 subjects. This is not intended to serve as a stopping rule, but rather an early submission indicator. A target of 92.5% of the first 100 subjects would need to experience success at 6 months to achieve Power greater than 80% and consideration of early submission.

## 12. RISK AND BENEFIT ANALYSIS

### 12.1 Potential Benefits

There is a growing trend toward the use of less invasive non-sternotomy incisions in all fields of cardiac surgery. While a median sternotomy provides the best access to the heart and great vessels, the same exposure could be accomplished with several smaller thoracotomy incisions. For patients who will require more than one cardiac operation (for example, VAD implantation as a bridge to transplantation), avoiding a median sternotomy in the first operation will reduce the surgical risk of a redo sternotomy in the following operations. Less-extensive mediastinal dissection in non-sternotomy incisions could reduce the prevalence and severity of postoperative bleeding. This is particularly important in VAD patients who require early anticoagulation therapy after implant. In addition, with a thoracotomy the pericardium remains mostly intact, which results in the stabilization of right heart function and possibly avoiding right heart dilatation during the procedure, especially when initially starting the HVAD® Pump. Many of these benefits also apply if the second operation is done via thoracotomy. The HVAD® Pump is designed to be implanted in the pericardial space. Its small design allows some versatility in placement and therefore does not limit the implant to a single surgical procedure. This implant versatility provides clinicians multiple options for implant and allows them to best match the patient with the procedure. There are some patients who may fare better with a thoracotomy rather than sternotomy. The potential benefit to the subject participating in this study is the implantation of a blood pump using a technique that is less obtrusive and that may be more comfortable. Morbidity rates and time of recovery may also be positively affected. The thoracotomy technique for implant may provide benefits not currently available with existing technology. The potential benefits as mentioned above include:

Potential Benefit	Thoracotomy Implant
Less invasive implant procedure	
 
• Smaller incisions
 
• Shorter hospitalization
 

Reduced bleeding	
 
• Less tissue trauma
 
• Virgin sternotomy at later procedure
 
• Thoracotomy at second procedure/device exchange
 

Reduced infection	
 
• Lower infection rates
 
• Less severe infections
 
• Virgin sternotomy at later procedure
 

Reduction of right heart failure	
 
• Pericardium more intact
 

Expand patient population	
 
• Include patients who may not tolerate a sternotomy
 

